8.4 Treatment Compliance

Treatment compliance is encouraged by patients receiving reminders from their eDiary for trial drug administrations. Patients are requested to enter details regarding trial drug administration (including date and time of the day as well as DUN) and injection site area used (i.e., abdomen, thigh) in the eDiary. Patients are to record PS use (including bag name, volume, infusion date, and duration) in the eDiary on an ongoing basis.

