3.1.4. Supportive analysis of primary endpoint derivation

The primary endpoint, actual weekly PS volume, will be derived as specified in Appendix A. The robustness of the primary analysis, with regard to the algorithm, will be explored through several supportive analyses, which each will address the impact of key algorithm elements. The analyses are considered 'supportive' as patients with missing PS entries continue in the trial, and no relevant intercurrent events are expected to trigger the missing entries.

Supportive estimator 1 is applying the derivation method specified in previous SAP versions (3.0 and 4.0) without any values carried forward. This is considered an extremely conservative estimate of the endpoint, as days without PS entries in the eDiary within a certain week will be imputed with the total weekly PS volume divided by the number of days of non-missing data.

Supportive estimator 2 and 3 assess the impact to the primary analysis by varying individual algorithm elements. That is by removing information collected through note-to-files, and increasing the minimum threshold necessary for calculating an endpoint with respect to percentage actual PS volume versus prescribed, respectively.

Supportive estimator 4 considers a continuum between main and supportive estimator 1, but without a threshold for setting the endpoint to missing. This is to explore the incremental impact of imputing missing PS entry days with either 0 L or the total weekly PS volume divided by the number of days of non-missing data.

To get an overview of the supportive estimators for the primary endpoint derivation, and each individual algorithm elements, please see Table 5.

Statistical Analysis Plan v6.0

Table 5 Overview of supportive analysis of primary endpoint derivation

	Main estimator	Supportive estimator 1	Supportive estimator 2	Supportive estimator 3	Supportive estimator 4
Algorithm element	Appendix A algorithm	SAP v3.0/4.0 algorithm	Appendix A algorithm w/o NTFs	Appendix A algorithm with less deviation from prescribed amount allowed	Tipping individual PS entry days
Threshold for setting endpoint missing	Yes, if actual PS entry days <7 and PS accounted for <90% vs prescribed PS	Yes, if actual PS entry days <4	Yes, if actual PS entry days <7 and PS accounted for <90% vs prescribed PS	Yes, if actual PS entry days <7 and PS accounted for <95% vs prescribed PS	No

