5.3. MISSING DATA AND DATA HANDLING RULES

Every effort will be made to collect all data at specified time points, according to the schedule of trial events. Reasons for withdrawal from the trial will be recorded on the eCRF.

For actual weekly PS volume, a detailed algorithm is included in Appendix A. In brief, for each visit, the actual weekly PS volume will be derived by using a valid 7-day period closest to the visit where

1. the actual weekly PS volume accounted for \geq 90% of prescribed weekly PS volume

or

2. there is at least one actual PS volume accounted for by the patient in the eDiary for each day in the valid 7-day period

For all post-baseline visits, the 7-day period is allowed to start up to 14 days before a visit, provided that it does not start before the previous visit. For baseline visits, the 7-day period is allowed to start up to 30 days before the baseline visit, provided that it does not start before the latest optimization visit. The Day 3 and Week 1 visits are not included in the calculations.

Note that, if the last PS prescription during the treatment period has been stopped more than 7 days prior to a visit, and there are no entries of actual PS volumes recorded by the patient in the eDiary within 7-days prior to this visit then the actual weekly PS volume will be set to zero.

The efficacy endpoints will be missing at visits, where no valid 7-days period can be found based on the above algorithm.

Any missing data during the trial prior to trial completion or discontinuation will remain as missing at that time point. However, several multiple imputation methods will be used to impute missing data for the primary efficacy endpoint as well as for the key secondary efficacy endpoints. See 5.3.1 for details of the multiple imputation method.

Imputation rules for the handling of missing data for PROs and health economic assessments will follow rules per each assessment manual.

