APPENDIX A. CALCULATION OF PRESCRIBED AND ACTUAL WEEKLY PS VOLUME

Prescribed weekly PS volume based on a 7-day period

The prescribed weekly PS volume (L/week) record per patient per nominal visit attended on or after Visit 1 (Day 1) will be calculated. The source is the prescribed PS volumes recorded in the eCRF by the investigator (SDTM.CM where CM.CMSCAT= 'PARENTERAL SUPPORT PRESCRIPTION').

A prescribed PS regimen consists of \geq 1'bag identifier(s)' (SDTM.CM.CMSPID). For each prescribed 'bag identifier' the volume (SDTM.CM.CMDOSE) is recorded in L/week. The prescription of a 'bag identifier' is considered current from the start date (CM.CMSDTC) until the end date (CM.CMENDTC) or until the end of trial if the last prescription end date is not available, hereafter referred to as a prescription period.

A prescription period might cover several visits. A PS prescription can be updated at the scheduled visits, but also in between visits at the discretion of the investigator.

If the end date of a current prescription period is the same as the start date of the next prescription period, the end date of the current period is set to the end date minus one day to avoid overlap.

The prescribed volume (AVAL) is derived as the sum of the prescribed volumes during the 7day period just prior to the visit divided by 7 (to account for the volumes being recorded in L/week), i.e. the period is defined from the visit date minus 1 to the visit date minus 7. Hereafter referred to as the *prescribed volume*.

Note that, if the last PS prescription during the treatment period has been stopped more than 7 days prior to a visit, the prescribed weekly PS volume will be set to zero at the relevant visit.

Actual weekly PS volume based on a valid 7-day period

An actual weekly PS volume (L/week) record per patient per nominal visit attended on or after Visit 1 (Day 1) will be derived, with the exception of visits Day 3 and Week 1 which will not be included in the ADaM dataset (see steps below).

The source is the actual PS volume records entered into the eDiary by the patient (SDTM.ZP), hereafter referred to as volume records.

The actual weekly PS volume (AVAL) is derived as the sum of the volume records (ZP.ZPSTRESN) in a valid 7-day period prior to the relevant visit. Hereafter referred to as the *actual volume*.

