The weekly PS volume accounted for is derived as the actual volume in a valid 7-day period prior to the relevant visit plus prescribed volumes documented not taken (via notes to file) during the same period. Hereafter referred to as the *volume accounted for*.

The relevant prescribed volume is derived as the sum of the prescribed volumes during the valid 7-day period divided by 7 (to account for the volumes being recorded in L/week). Hereafter referred to as the *relevant prescribed volume*.

The steps to select a valid 7-day period and derive AVAL related to an attended visit are as follows:

- 1. The first period considered will be the 7-days period from the visit date minus 1 day to the visit date minus 7 days.
- 2. A valid period cannot start before the previous visit for post-baseline visits (before the last optimization visit for baseline visits). If the considered period starts before the previous visit date then, AVAL will be set to missing, ANLxxFL is set to ' ' and ANLxxREA = "Period starts before previous visit" and the loop stops.

Note that, the exemption to this rule will be that a Week 1 valid period will be allowed to start prior to the date of visit Day 3 (which is not included in the dataset) or baseline visit, and Week 2 valid period will be allowed to start prior to the dates of visits Week 1 or Day 3 (which is not included in the dataset).

- 3. Else, if there is at least one volume accounted for at each day in the eDiary for the period, then the period is considered valid, AVAL is derived as specified above, and ANLxxFL is set to 'Y' and the loop stops.
- 4. Else, if for the period, the volume accounted for is ≥ 90% of the relevant prescribed volume, then the period is considered valid, AVAL is derived as specified above, and ANLxxFL is set to 'Y' and the loop stops.

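### A week with one PS entry per day is accepted with no check against prescribed volume, and neither supportive estimator 3, the rest of SAP Table 5 nor the 14-day analysis tests this

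*SAP*

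**What the plan says.** The endpoint value is "derived as the sum of the volume records (ZP.ZPSTRESN) in a valid 7-day period prior to the relevant visit" (SAP Appendix A). A 7-day window becomes valid by one of two routes, tried in order:

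- Step 3: "if there is at least one volume accounted for at each day in the eDiary for the period, then the period is considered valid". The search then stops.
- Step 4, tried only if step 3 fails: "the volume accounted for is ≥ 90% of the relevant prescribed volume".

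SAP 5.3 gives the same two conditions as alternatives, the second being that "there is at least one actual PS volume accounted for by the patient in the eDiary for each day in the valid 7-day period". Table 5 in SAP 3.1.4 is consistent with this. Its rule for setting the endpoint to missing is "Yes, if actual PS entry days <7 and PS accounted for <90% vs prescribed PS" for the main estimator and supportive estimator 2, and "Yes, if actual PS entry days <7 and PS accounted for <95% vs prescribed PS" for supportive estimator 3.

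Diary entries are made per bag. Protocol 8.4 states: "Patients are to record PS use (including bag name, volume, infusion date, and duration) in the eDiary". Appendix A allows a prescribed regimen to consist of more than one bag.

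**The concern.** One entry on a day does not show that the day is complete when a patient infuses more than one bag. For a window with an empty day, the SAP treats less than 90% of prescribed volume accounted for as too incomplete to use. For a window with an entry on all 7 days it applies no volume standard. A missing second bag then counts as volume not infused, and after baseline that reads as PS reduction. At baseline the same omission works the other way, because it lowers the starting value.

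The value feeds the primary endpoint, the Week 12 endpoint and the 20% responder endpoint. SAP 3.1.4 sets out to test the key elements of the algorithm, and estimator 3 is the one aimed at agreement with prescription. Its two conditions must both hold before a week is set to missing, so it cannot act on a week with 7 entry days.

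**Working it through.** **1. What each planned analysis does with a 7-entry week**

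- Main estimator and supportive estimator 2: missing only if entry days are below 7 and the volume is below 90%. With 7 entry days the first condition fails, so the week is accepted. Estimator 2 only drops notes to file.
- Estimator 1: missing only below 4 entry days; it fills only days with no entry.
- Estimator 3: missing only if entry days are below 7 and the volume is below 95%. Accepted.
- Estimator 4: no missingness threshold; it varies only the value given to days with no entry.
- 14-day derivation (Appendix A): same validity rules, so the same bypass.
- Delta tipping-point analysis (SAP 3.1): shifts only imputed values.
- Prescribed weekly PS volume and prescribed weaned-off (SAP 3.4): taken from the eCRF, so independent of diary completeness.

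**2. The rules applied to example weeks**

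The regimens are assumed. Only the first 7-day window is considered, there are no notes to file, and 14 L/week is prescribed. The last column requires at least 90% of prescribed volume whatever the number of entry days; 95% gives the same answers.

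| Diary week | Recorded | % of prescribed | Main | S1 | S2 | S3 | S4 | Proposed rule |
|---|---|---|---|---|---|---|---|---|
| A: two 1 L bags daily, one recorded each day | 7 × 1 = 7 L | 50.0 | 7 | 7 | 7 | 7 | 7 | not valid |
| B: as A, second bag omitted on 3 of 7 days | 4 × 2 + 3 × 1 = 11 L | 78.6 | 11 | 11 | 11 | 11 | 11 | not valid |
| C: two 1.4 L bags on 5 days, one recorded each time, no entry on the other 2 days | 5 × 1.4 = 7 L | 50.0 | not valid | 9.8 | not valid | not valid | 7.0 to 9.8 | not valid |

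In B, with a true 14 L at both times and baseline fully recorded, the apparent reduction is 1 − 11/14 = 21.4%, above the 20% threshold. Weeks A and C lose the same 7 L. C is caught and A is not, solely because C has days with no entry.

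**3. Scale against the planned trial**

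The documents give no figure for under-recording, so the planning assumptions serve as the yardstick: differences of 2.2 and 2.0 L/week, SD 2.62, 36 per arm, two-sided 0.025 per comparison (Protocol 12.7, SAP 2.6).

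Plan's figure first. SE = 2.62 × √(2/36) = 0.617. Either-comparison power = 1 − P(both tests fail), bivariate normal with correlation 0.5 from the shared placebo arm. Result: 95.8% (95.1% by simulated t-test), against 95% stated. It reproduces.

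Now let a share q of patients omit v L/week after baseline. The mean of an affected arm shifts by q × v, and its variance becomes 2.62² + q(1 − q)v². Both q and v are assumptions; v = 3.5 is a 0.5 L bag daily and v = 7 a 1 L bag daily.

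| v (L/week) | q | Shift q × v | Null rejection at nominal 2.5%, excess in one active arm only | Either-comparison power, equal in all arms |
|---|---|---|---|---|
| 3.5 | 5% | 0.18 | 3.1% | 94.2% |
| 3.5 | 10% | 0.35 | 4.8% | 92.7% |
| 3.5 | 20% | 0.70 | 11.9% | 89.9% |
| 7 | 5% | 0.35 | 4.6% | 88.7% |
| 7 | 10% | 0.70 | 10.5% | 81.5% |
| 7 | 20% | 1.40 | 33.3% | 70.2% |

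If the excess lies in placebo instead, the shift is subtracted from the planned difference. At q = 10% and v = 3.5 it becomes 2.2 − 0.35 = 1.85 or 2.0 − 0.35 = 1.65 L/week, which is conservative.

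**The case against.** The strongest reply is that the sites, not the algorithm, are the control. Investigators must review the diaries routinely and resolve discrepancies (Protocol 11.2.1), PS data are checked at every visit (11.2.2), adherence to the PS regimen is recorded at treatment visits (10.4), and the Week 24 volume gets special effort (7.5). The 20% response also needs both Weeks 20 and 24, so one bad week does not create a responder. All this makes gross under-recording less likely. It does not show in the analysis whether any remained.

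Some stronger readings do not hold:

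- *Nothing in the plan tests this.* The prescribed-volume analysis uses the primary methodology and does not depend on the diary, so unrecorded bags would make actual and prescribed results diverge. It is still indirect: it cannot separate bags not recorded from bags not taken, and SAP 3.4 plans no 20% response on prescribed volume.
- *The lack of an upper limit makes unrecorded bags count as reduction.* An upper limit concerns over-recording, which would inflate reduction only at baseline. There the ±10% stability criterion (Protocol 7.4) gives partial protection, although the derivation does not itself apply it.
- *The bypass favours glepaglutide.* In a double-blind trial, equal under-recording mainly adds noise. If patients who stay on daily PS are mostly on placebo, their unchecked omissions shrink the difference. Even the contrast between daily and other patients assumes no entry on PS-free days. The documents do not say whether a zero is entered; if it is, step 3 covers everyone alike.
- *The main derivation must apply the 90% check.* The estimand is actual volume under a treatment-policy strategy. True deviation from prescription is outcome data, so that change would be a trade-off and not a correction.

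**Conclusion.** The gap is real and narrow. Any week with an entry on all 7 days bypasses comparison with prescribed volume, and no Table 5 estimator or 14-day analysis can reveal a partly recorded day. Estimator 3 fails at its stated purpose for exactly those weeks. The effect on one patient can be large: 3 L of 14 L/week in example B, 7 L in A. The effect on the treatment contrast is unknown in size and direction, because the documents give neither the frequency of under-recording nor its split by arm. The tabulated shifts of 0.18 to 1.40 L/week, and the rejection and power figures beside them, rest wholly on assumed shares and volumes. They show what a check should be able to rule out and are not estimates of bias. The point justifies a corrected supportive analysis and a tabulation; it does not call the primary analysis into question.

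**What to change.** 1. In Table 5, redefine supportive estimator 3, or add an estimator, so that a window is valid only if the volume accounted for, including notes to file, is at least 95% (or 90%) of the relevant prescribed volume, regardless of the number of entry days. Keep the existing Appendix A rule for weeks with no prescribed PS. Do not simply change the conjunction in the Table 5 cell from 'and' to 'or': that would set every week with fewer than 7 entry days to missing, however complete its volume.
2. Tabulate by arm and visit, including baseline, the windows accepted under step 3 with less than 90% or more than 110% of prescribed volume accounted for. This shows whether the problem exists, whether it differs by arm, and whether over-recording occurs at baseline.
3. Leave the main derivation as it is.

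Cost: SAP wording, one logic change in the derivation program and one table, all from data already collected. Downside: genuine but undocumented under-use in 7-entry weeks becomes missing in that supportive analysis only. Documented under-use still passes, because volume noted as not taken counts as accounted for.

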6.2 Overall Trial Design

After providing informed consent, and initial confirmation of eligibility during the 2-week Screening period, patients will enter a PS Optimization and Stabilization Phase before baseline measurements are performed. An individual drinking menu will be defined by the patient and the Investigator during the Screening Period and until the end of the Optimization Phase. All patients will be equipped with an electronic diary (eDiary) for recording trial relevant data/information. Unless otherwise specified, baseline is defined as Day 1, prior to first dosing of trial product. PS optimization consist of 2 rounds, which limits the Optimization Phase to a maximum duration of 4 weeks (\pm 4 days). If optimization cannot be shown during the 4-week period, a second Optimization Phase of up to 4 weeks (\pm 4 days) is allowed. The last Optimization Phase visit can be combined with the first visit in the Stabilization Phase if the patient is considered optimized.

During the Optimization Phase, the Investigator and the patient may redefine and optimize the individual drinking menu to best fit the patient's needs. Once the drinking menu has been set at

the end of the Optimization Phase, no additional modification to the drinking menu will be allowed and the patient will be required to adhere to the drinking menu during the 48-hour balance periods throughout the remainder of the trial.

Stabilization Phase

The Stabilization Phase has a minimum duration of 2 weeks and a maximum duration of 4 weeks (± 4 days). The last visit of the Optimization Phase can also be the first visit of the Stabilization Phase. Prior to the Stabilization Phase visit, the patient must measure his/her urine volume over 48 hours while adhering to the pre-defined drinking menu and report the urine volume and oral fluid intake in the eDiary. Patients will be evaluated every 2 weeks (± 4 days) during the Stabilization Phase and will need to fulfill the stability criteria (see below) before the patient can be randomized. If stability cannot be shown during the 4-week period due to unforeseen events such as infections, illness or similar, a second Stabilization Phase of up to 4 weeks (± 4 days) is allowed.

The baseline value for urine volume (L per day) will be defined as the average of the last two 48-hour urine volumes from the Stabilization Phase (e.g., visits St1 and St2 or visits St2 and St3).

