The baseline PS volume (L/week) will be defined as the actual PS volume received during the 7-day period prior to Visit 1 (Day 1). No changes in the prescribed weekly PS volume or schedule is allowed during the Stabilization phase.

A patient will be considered stable if all of the following criteria are met:

- Actual PS usage (volume and content) matches prescribed PS ($\pm 10\%$ deviation in total volume is acceptable) and
- 48-hour urine volumes at 2 consecutive visits within a 2-week interval (± 4 days, i.e., visits should be 10 to 18 days apart) are similar (a maximum of $\pm 25\%$ deviation is acceptable), while the oral fluid intake is constant (the two 48-hour oral intakes differ less than 10%) and maximum 3.5 L per day, and
- Urine volume is on average ≥ 1 L per day and ≤ 2.5 L per day.

The Investigator and Medical Monitor must both agree and approve that the patient has met the criteria to be considered stable after completing the Stabilization Phase. See [Section 8.7](#) for more details.

Main Trial Period

Visit 1 is done within 2 weeks after the last Stabilization Phase visit. If done on the same day, Visit 1 lab samples should be drawn. All eligible patients who complete the Optimization and Stabilization Phases will be randomized in a 1:1:1 manner to receive 2 SC injections weekly of either: a) glepaglutide 10 mg twice weekly, b) glepaglutide 10 mg once weekly and placebo once weekly, or c) placebo twice weekly for the following 24 weeks.

During the 24-week Treatment Phase, PS need will be evaluated based on the 48-hour balance periods with a fixed drinking menu (individually pre-defined during the Optimization Phase) and measurements of urine volume done prior to each trial visit (except for Visit 2-phone assessment).

The actual volume of PS will be recorded on an ongoing basis in the eDiaries by the patients. The Investigator will record in the eCRF the type, content, and volume of the PS being used. Once trial drug treatment is initiated, PS volume can be adjusted at trial visits (at Weeks 1, 2, 4, 8, 12, 16, 20, and 24) if the criteria for adjustment are met and according to a predefined algorithm ([Section 8.7.4](#)).

The Investigator may arrange unscheduled visits (preceded by a 48-hour balance period) if he or she considers the visits to be needed based on medical judgement to assess PS volume needs.

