10.3 Stabilization Phase

The Stabilization Phase visits should be scheduled approximately 2 to 4 weeks (\pm 4 days, i.e., visits should occur 10 to 18 days apart) after the Optimization Phase visit. The first Stabilization Phase visit can be combined with the last Optimization Phase visit if the patient is considered optimized. If stability cannot be shown during the 4-week period due to unforeseen events such as infections, illness or similar, a second Stabilization Phase (St4, St5, etc.) of up to 4 weeks (\pm 4 days) is allowed. Prior to the patient's planned visit, the Investigator should review the patient's eDiary information to ensure that the necessary data are available. If the information was not

entered into the eDiary, the patient's trial visit should be rescheduled to ensure availability of 48-hour balance measurements.

During the Stabilization Phase visit(s), the following assessments will be performed:

- Complete PRO questionnaires (preferably the SBS-I followed by EQ-5D-5L) at start of stabilization phase
- Record body weight
- Record any procedures and changes to concomitant medications
- Record vital signs (heart rate, systolic and diastolic blood pressure, and body temperature)
- Record AEs
- Collect urine sample for urinalysis
- Obtain blood samples for:
 - hCG pregnancy test (for females of childbearing potential only)
 - Hematology
 - Biochemistry
- Review eDiary information for:
 - PS use
 - 48-hour oral fluid intake
 - 48-hour urine volume output
 - 48-hour bowel movements/stoma bag emptying
- Record adherence to PS regimen (including weekly schedule, volume, and content) and drinking menu
- Instruct patient in eDiary completion of number of bowel movements (CiC patients) /number of stoma bags emptied (stoma patients) during the 48-hour balance periods

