If the loop is not stopped in steps 1, 2, 3 and 4 then a new 7-day period is defined from the visit date minus 2 days to visit date minus 8 days and the loop is re-started (steps 2, 3, and 4). For post-baseline visits, the loop can be re-started until the new 7-day period is from the visit date minus 8 days to the visit date minus 14 days. For baseline visits, the loop can be re-started until the new 7-day period is from the visit date minus 14 days. For baseline visits, the loop can be re-started until the new 7-day period is from the visit date minus 24 days to the visit date minus 30 days. If the loop reaches earliest allowed period without stopping then AVAL will be set to missing, ANLxxFL =' ' and ANLxxREA = "No valid period identified".

Note that, if there are 7 days without relevant prescribed PS prior to a visit, then the period will be considered valid, AVAL will be derived as the sum of available volumes found in the 7-day prior to the visit, and the ANLxxFL will be set to 'Y'. If and there are no PS volume entries in the eDiary, AVAL will be set to 0 (zero).

Note: that for calculating \geq 90% volume accounted for, the relevant prescribed volume will be calculated using the same time-period as the actual volume, in contrast to the prescribed parameter described above, which strictly uses the values in the period visit date minus 1 day to visit date minus 7 days for the derivation.

Prescribed and actual weekly PS volume based on a 14-day period

The same rules as stipulated above apply when calculating the **actual** weekly PS volume based on a 14-day valid period, except that the loop can be re-started until the 14-day period is from the visit date minus 28 days to the visit date minus 15 days.

Note that, if the last prescription end date is more than 14 days prior to the visit, and there are no PS volume entries in the eDiary, the actual weekly PS volumes (AVAL) will be set to 0, and ANLxxFL will be set to 'Y'.

Note that, for the actual volumes the Day 3, Week 1 and Week 2 visits will not be included in the dataset, and hence the Week 4 valid 14-day period is allowed to start before the date of any of these visits.

The **prescribed** weekly PS volume will be derived as described above but based on the period from the visit date minus 1 to the visit date minus 14. Note that, if the last prescription end date is more than 14 days prior to the visit, the prescribed weekly PS volumes (AVAL) will be set to 0, and ANLxxFL will be set to 'Y'.

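### Patients with only 10 to 13 days between the last optimization visit and Visit 1 have no valid 14-day baseline PS volume, so the 14-day sensitivity analyses replace an observable baseline

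*SAP*

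**What the plan says.** **SAP.** Appendix A selects a valid period by stepping a window back from the visit, one day at a time. Step 2 limits how far it may go: "A valid period cannot start before the previous visit for post-baseline visits (before the last optimization visit for baseline visits". If the window breaches that limit, the value is set to missing and the loop stops. SAP Section 5.3 repeats the limit for baseline: "provided that it does not start before the latest optimization visit". The 14-day derivation takes over these rules and resets the limit of the search: "the loop can be re-started until the 14-day period is from the visit date minus 28 days to the visit date minus 15 days". The only relaxation of step 2 written for 14 days concerns Week 4; there is none for baseline.

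**Protocol.** Section 6.2 allows the run-in phases to share a visit: "The last visit of the Optimization Phase can also be the first visit of the Stabilization Phase". The two visits that establish stability need only meet this condition: "visits should be 10 to 18 days apart". Visit 1 follows within two weeks of the last stabilization visit and may coincide with it: "If done on the same day, Visit 1 lab samples should be drawn".

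**Where the 14-day volume is used.** It enters sensitivity estimator 3 of the primary endpoint (SAP 3.1) and, by reference to the same estimators, the Week 12 change. It also enters the sensitivity analysis of the binary key secondary endpoints (SAP 3.2, Table 6) and supporting analyses of energy content (SAP 3.4).

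**The concern.** A 14-day window needs 14 days of post-optimization diary, and the protocol does not guarantee that many before Visit 1. A compliant patient with no diary gaps can therefore be given a missing baseline by the rule itself.

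The 14-day analyses exist to show whether the result depends on the length of the measurement window. If some patients enter them with a baseline that is not their own, a difference from the 7-day result could partly reflect run-in length and baseline substitution instead of window length.

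**Working it through.** **Inputs**
- Spacing of the two qualifying stabilization visits: 2 weeks ± 4 days, so 14 − 4 = 10 to 14 + 4 = 18 days. This reproduces the range in Protocol 6.2.
- Last optimization visit to first stabilization visit: 0 days if combined (Protocol 6.2).
- Last stabilization visit to Visit 1: 0 to 14 days (Protocol 6.2).
- Farthest window start at baseline: 30 days back for the 7-day volume, 28 days back for the 14-day volume (Appendix A).

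**Shortest gap g from last optimization visit to Visit 1**

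g = 0 + 10 + 0 = 10 days.

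**Admissible windows**

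A window of length L that ends k days before Visit 1 starts k + L − 1 days before it. Step 2 requires k + L − 1 ≤ g. The number of admissible windows is max(0, min(g, limit) − L + 1).

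| g (days) | 7-day windows | 14-day windows |
|---|---|---|
| 10 | 4 | 0 |
| 11 | 5 | 0 |
| 12 | 6 | 0 |
| 13 | 7 | 0 |
| 14 | 8 | 1 |
| 18 | 12 | 5 |
| 28 | 22 | 15 |

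At g = 10 the first 14-day window starts 4 days before the last optimization visit, so the loop stops on its first pass. When the two phases share a visit and stabilization visits are 10, 11, 12 or 13 days apart, Visit 1 must come at least 4, 3, 2 or 1 days after the last stabilization visit for any window to fit.

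**How many patients?** The documents give no distribution of intervals. The following are assumptions, and apply only to patients with two stabilization visits whose last optimization visit is the first of them. Spacing is taken as uniform over the nine values from 10 to 18 days.
- Visit 1 always on the day of the last stabilization visit: 4 of 9 combinations give g < 14 (44%).
- Lag uniform over 0 to 3 days: (4 + 3 + 2 + 1) of 9 × 4, or 10 of 36 (28%).
- Lag uniform over 0 to 14 days: 10 of 9 × 15 = 135 (7%).
- All gaps 14 days or more: 0%.

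**What then happens to the missing baseline**
- Estimator 3 uses multiple imputation. The note after SAP Table 3 has baseline imputed from a model on FAS patients.
- The 14-day binary analyses do not use multiple imputation. The same note gives other analyses the FAS mean baseline, whereas SAP Table 6 makes missing data a non-response. Under the first, a patient whose own baseline is at or below 0.8 × the FAS mean meets the 20% criterion with no reduction at all. Under the second, a real reduction is not counted.
- The weaned-off endpoint is zero volume at Week 24 and needs no baseline.

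**The case against.** **The two-week minimum.** Protocol 6.2 also states: "The Stabilization Phase has a minimum duration of 2 weeks and a maximum duration of 4 weeks". Section 7.4 asks for a stable volume over at least two weeks at randomization. Read as a strict 14 days, exactly one window fits, because it starts on the last optimization visit and not before it. This stands as a competing reading. It does not settle the matter: the schedule of assessments gives 2 to 4 weeks ± 4 days, and Section 7.4 itself defines stability by visits 10 to 18 days apart. Protocol 10.3 uses the same spacing: "i.e., visits should occur 10 to 18 days apart) after the Optimization Phase visit".

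**Same-day Visit 1 may be rare.** Protocol 10.4 lets Visit 1 be scheduled once the investigator and the medical monitor have both reported stability. That is fair, and it is why no share of patients can be asserted.

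**The exclusion is deliberate.** SAP Section 9 explains that optimization-period data are barred because patients are not yet considered stable. That is sound and the fix keeps it.

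**Stronger readings to avoid**
- A reader might infer that true responders will be scored as failures. That is only one of two readings, since the note after SAP Table 3 points to the FAS mean instead.
- A reader might infer that close to half of the patients lose their baseline. The 44% rests on assumed scheduling within a subset.
- A reader might infer bias in favour of one arm. The gap is fixed before dosing and, under blinded randomization, should be unrelated to treatment.
- A reader might infer that baseline is the only 14-day value at risk. With scheduled visits inside their windows, the smallest gap from Week 8 on is 14 days (for example (169 − 7) − (141 + 7) = 14 for Week 20 to Week 24). That leaves no slack, and step 2 does not say whether an unscheduled visit counts as the previous visit.

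**Conclusion.** The concern holds, as a minor point. For any gap of 10 to 13 days, Appendix A as written sets the 14-day baseline to missing although the 7-day rule can observe it. In estimator 3 the value is imputed from other patients. In the 14-day analyses of 20% response and of reduction in PS days, the patient's own baseline is not used under either reading of the SAP.

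This rests on reading the 10-to-18-day spacing and the ± 4 days as permitting a stabilization phase shorter than 14 days. The effect is confined to the 14-day sensitivity and supporting analyses.

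**What to change.** Add to the 14-day part of Appendix A: when fewer than 14 days lie between the last optimization visit and Visit 1, the valid 7-day baseline serves as the 14-day baseline. Protocol 6.2 forbids changes to prescribed weekly PS volume or schedule during stabilization, so the 7-day value describes the same regimen. Report the number of such patients by arm.

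Do not scale a partial second week. With PS on days 1, 3 and 5 of the week, a 10-day window holds 4 or 5 infusion days. Scaled, that is 4 × 7/10 = 2.8 or 5 × 7/10 = 3.5 per week against a true 3, an error of −7% or +17% with a perfect diary. That is large next to a 20% response threshold.

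It would also help to state which rule governs a missing baseline in the binary analyses.

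The cost is a sentence or two and minor programming. The downside is that a few baselines in the 14-day analysis rest on 7 days, which mixes window lengths in an analysis meant to test window length. The count by arm lets the reader judge whether that matters.
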